9.4.2 Safety Analyses

AEs/SAEs will be coded and tabulated using the current version (as of study start) of Medical Dictionary for Regulatory Activities (MedDRA). Each AE will be classified by System Organ Class (SOC) and preferred term.

Treatment-emergent AEs (TEAEs) are defined as those AEs that started on or after the dose of study medication or worsened after the dose of study medication. Only TEAEs will be summarized. The incidence of TEAEs will be presented by the number and percent of subjects who experienced the TEAE.

Each subject will be counted only once in the incidence for each term (overall incidence, SOC, or preferred term). The incidence of treatment-related TEAEs will be summarized by SOC and preferred term. The incidence of serious TEAEs, and the incidence of treatment-related SAEs will be tabulated similarly.

In addition, the incidence of TEAEs will be summarized by SOC, preferred term, and maximum severity based on CTCAE grade, by relationship to NTLA-5001.

Clinical laboratory data, ECG parameters and other safety data will be summarized with descriptive statistics. Details will be described in the SAP.

10 DATA MONITORING COMMITTEE (DMC)

An independent DMC will be established to review any events that meet pausing criteria and to review completed dose escalation safety data prior to enrolling the expansion population. The DMC will include, at a minimum, 2 physicians with experience treating hematologic malignancies with T cell therapy (who are not clinical trial investigators) and 1 statistician.

Proceeding to expansion will be decided by the Sponsor, with the DMC providing a recommendation. In addition, consultation with the DMC may occur at any time to review data to manage subject safety. All decisions by the DMC will be communicated electronically to the trial Investigators within 48 hours of the Sponsor's notification. Details are included in the DMC Charter.

11 SUPPORTING DOCUMENTATION AND OPERATIONAL CONSIDERATIONS

11.1 Regulatory, Ethical, and Study Oversight Considerations

11.1.1 Regulatory and Ethical Considerations

This study will be conducted in accordance with the protocol and with the following:

- Consensus ethical principles derived from international guidelines including the Declaration of Helsinki and Council for International Organizations of Medical Sciences (CIOMS) International Ethical Guidelines
- Applicable ICH GCP Guidelines
- Applicable laws and regulations

The protocol, protocol amendments, ICF, Investigator's Brochure, and other relevant documents (e.g., subject recruitment advertisements) must be submitted to an IRB/IEC for review and approval before the study is initiated at a clinical study site.

Any substantial amendments to the protocol will require regulatory and IRB/IEC approval before implementation of changes made to the study design at the clinical study site, except for changes necessary to eliminate an immediate hazard to study subjects.

If there is significant public emergency (e.g., pandemic, environmental, etc.), the continuity of clinical study conduct, and oversight may require implementation of temporary or alternative mechanisms. Examples of such mechanisms may include, but are not limited to, any of the following: phone contact, virtual visits, telemedicine visits, online meetings, noninvasive remote monitoring devices, use of local clinic or laboratory locations, and home visits by skilled staff. No waivers will be granted for study entry criteria. All temporary mechanisms utilized, and deviations from planned study procedures are to be documented as being related to the public emergency and will remain in effect only for the duration of the public emergency.

The investigator will be responsible for the following:

- Providing written summaries of the status of the study to the IRB/IEC annually or more frequently in accordance with the requirements, policies, and procedures established by the IEC.
- Taking appropriate urgent safety measures to protect subjects against any immediate hazard and notify Sponsor promptly.
- Notifying the IEC of SAEs or other significant safety findings as required by IEC procedures and in parallel the Sponsor.
- Providing oversight of the conduct of the study at the site and adherence to requirements of 21 Code of Federal Regulations (CFR), ICH guidelines, the IEC, European directive 2001/20 and its replacement regulation 536/2014 for clinical studies when the latter comes into operation, and all other applicable local regulations.

New information that becomes available and is relevant to the management and care of a participating subject will be communicated promptly to all participating investigators.

11.1.2 Financial Disclosure

Investigators and sub-investigators will provide the Sponsor with sufficient, accurate financial information, as requested, to allow the Sponsor to submit complete and accurate financial certification or disclosure statements to the appropriate regulatory authorities. Investigators are responsible for providing information on financial interests during the course of the study and for 1 year after completion of the study.

11.1.3 Informed Consent Process

The investigator or his/her representative will explain the nature of the study to the subject and answer all questions regarding this study. Prior to any study-related screening procedures being performed on the subject, the informed consent statement will be reviewed, voluntarily signed and dated by the subject or his/her guardian or legal representative, the person who administered the informed consent and any other signatories according to local requirements. A copy of the signed ICF will be given to the subject and the original will be placed in the subject's medical record. An entry must also be made in the subject's dated source documents to confirm that informed consent process was completed and signed informed consent was obtained prior to any study-related procedures and that the subject received a signed copy.

The signed consent forms will be retained by the investigator and made available (for review only) to the study monitor and auditor, regulatory authorities and other applicable individuals upon request.

A new informed consent is required to be signed prior to any rescreening activities.

11.1.3.1 Supply of New and Important Information Influencing the Subject's Consent and Revision of the Written Information

The investigator or his/her representative will inform the subject orally as soon as possible whenever new information becomes available that may be relevant to the subject's consent or may influence the subject's willingness to continue to participate in the study (e.g., report of serious adverse drug reaction). The communication must be documented in the subject's medical records and must document whether the subject is willing to remain in the study or not.

The investigator must update their ICF and submit it for approval to the IEC. The investigator or his/her representative must obtain written informed consent from the subject on all updated ICFs throughout his/her participation in the study. The investigator or his/her designee must re-consent subjects with the updated ICF even if relevant information was provided orally. The investigator or his/her representative who obtained the written informed consent and the subject should sign and date the ICF. A copy of the signed ICF will be given to the subject and the original will be placed in the subject's medical record. An entry must be made in the subject's records documenting the re-consent process.

11.1.4 Data Protection

The Sponsor considers individual subject information obtained as a result of this study to be confidential and processing of such data should be performed in strict adherence to regional data protection laws. No identified or identifiable personal data should be disclosed by anyone involved in the performance of the clinical study without justifiable reasons and in compliance with the applicable laws and rules. The following measures will be implemented to lawfully process personal data including health-related data arising from the study:

- A subject will be assigned a unique identifier by the Sponsor. Any subject's records or datasets that are transferred to the Sponsor will contain the identifier only; subject names or any information that would make the subject identifiable will not be transferred.
- The subject is informed of the specific purpose of processing personal health-related data arising from the study in order for the subject to give the consent freely, unambiguously and specifically in accordance with the requirements set out in the applicable data protection law.
- The subject is informed that his/her medical records containing health-related information may be accessed by the Sponsor, Sponsor's authorized representative(s), the IEC members, and representatives of the regulatory authorities for a specific and legitimate purpose relating to medical research.
- Internal policy has been established to guide all Sponsor personnel and contractors engaged by the Sponsor involved in the performance in the study to ensure compliance with the applicable data protection laws. In addition, a Privacy Statement has been developed consistent with the requirements set out in Article 13 of the General Data Protection Regulation (European Union [EU] Regulation 2016/679), providing detailed information concerning this collection and processing of personal data which will be applied to all trial sites.

11.1.5 Notification of Serious Breach

The Sponsor is responsible for ensuring compliance of the study with the applicable laws and the approved study protocol. The Sponsor will notify the relevant regulatory authority or authorities of a serious breach of the applicable laws or the approved study protocol within required timeframe of becoming aware of the breach. Whether or not a notification should be submitted will be based on an assessment of whether the breach will likely affect to a significant degree the safety and rights of a trial subject or the reliability and robustness of the data generated in the clinical trial. To this end, the trial sites, investigators and the relevant ancillary staff as well as contractors are required to fully cooperate with the Sponsor to render such an assessment.

11.1.6 Data Management

Data Management will be coordinated by the Sponsor. All study-specific processes and definitions will be documented by Data Management. eCRF completion will be described in the eCRF completion guidelines. Coding of medical terms and medications will be performed using MedDRA and World Health Organization Drug Dictionary, respectively.

All subject data relating to the study will be recorded on eCRFs unless transmitted to the Sponsor or designee electronically (e.g., laboratory data). The investigator is responsible for verifying that data entries are accurate and correct by electronically signing the eCRF.

11.1.7 Clinical Monitoring

The Sponsor or delegated CRO is responsible for monitoring the clinical study to ensure that subject's human rights, safety, and well-being are protected, that the study is properly conducted in adherence to the current protocol and GCP, and study data reported by the investigator/sub-investigator are accurate and complete and that they are verifiable with study-related records such as source documents. The Sponsor is responsible for assigning study monitor(s) to this study for proper monitoring. They will monitor the study in accordance with planned monitoring procedures.

Retention of study documents will be governed by the Clinical Trial Agreement.

11.1.8 Protocol Deviations

A protocol deviation is generally an unplanned excursion from the protocol that is not implemented or intended as a systematic change. The investigator is responsible for ensuring the study is conducted in accordance with the procedures and evaluations described in this protocol and must protect the rights, safety, and welfare of subjects. The investigator should not implement any deviation from, or changes of, the protocol, unless it is necessary to eliminate an immediate hazard to trial subjects.

For the purposes of this protocol, deviations requiring notification to Sponsor are defined as any subject who:

- Entered into the study even though he/she did not satisfy entry criteria.
- Developed withdrawal criteria during the study and not withdrawn.
- Received incorrect dose or infusion error (e.g., exceeds time requirement for administration of infusion).
- Received excluded concomitant treatment.

When a deviation from the protocol is identified for an individual subject, the investigator or designee must ensure the Sponsor is notified. The Sponsor will follow-up with the investigator, as applicable, to assess the deviation and the possible impact to the safety and/or efficacy of the subject to determine subject continuation in the study.

If a deviation impacts the safety of a subject, the investigator must contact the Sponsor immediately.

The investigator will also assure that deviations meeting IRB/IEC and applicable regulatory authorities' criteria are documented and communicated appropriately. All documentation and communications to the IRB/IEC and applicable regulatory authorities will be provided to the Sponsor and maintained within the Trial Master File.

NOTE: Other deviations outside of the categories defined above that are required to be reported by the IRB/IEC in accordance with local requirements will be reported, as applicable.

11.1.9 Source Documents

- The investigator must maintain accurate documentation (source data) that supports the information entered in the eCRF including description of procedures for the identification of data to be recorded directly on the CRF considered as source data.
- The investigator is responsible for ensuring that the source data are attributable, legible, contemporaneous, original, accurate and complete whether the data are hand-written on paper or entered electronically
- Source documents provide evidence for the existence of the subject and substantiate the integrity of the data collected. Source documents are filed at the investigator's site.
- Data entered in the eCRF that are transcribed from source documents must be consistent with the source documents or the discrepancies must be explained. The investigator may need to request previous medical records or transfer records, depending on the study. Also, current medical records must be available.
- The investigator must permit study-related monitoring, audits, IRB/IEC review, and regulatory agency inspections, and provide direct access to source data documents.

11.1.10 Quality Assurance

The Sponsor is implementing and maintaining quality assurance and quality control systems with written Standard Operating Procedures (SOPs) to ensure that trials are conducted, and data are generated, documented, recorded, and reported in compliance with the protocol, GCP, and applicable regulatory requirement(s).

The Sponsor or Sponsor's designee may arrange to audit the clinical study at any or all investigational sites and facilities. The audit may include on-site review of regulatory documents, CRFs, and source documents. Direct access to these documents will be required by the auditors.

11.1.11 Study and Site Start and Closure

The study start date is the date on which the clinical study will be open for recruitment of subjects.

The end of trial in all participating countries is defined as the Last Subject's Last Visit.

The Sponsor reserves the right to close the study site or terminate the study at any time for any reason at the sole discretion of the Sponsor. Study sites will be closed upon study completion. A study site is considered closed when all required documents and study supplies have been collected and a study-site closure visit has been performed.

The investigator may initiate study-site closure at any time, provided there is reasonable cause and sufficient notice is given in advance of the intended termination.

Reasons for the early closure of a study site by the Sponsor or investigator may include but are not limited to:

- Failure of the investigator to comply with the protocol, the requirements of the IRB/IEC or local health authorities, the Sponsor's procedures, or GCP guidelines

- Inadequate recruitment of subjects by the investigator
- Discontinuation of further study intervention development

If the study is prematurely terminated or suspended, the Sponsor will promptly inform the investigators, the IECs/IRBs, the regulatory authorities, and any CRO used in the study of the reason for termination or suspension, as specified by the applicable regulatory requirements. The investigator will promptly inform the subject and must ensure appropriate subject therapy and/or follow-up.

If the ITL-5001-CL-001 study is prematurely terminated or suspended, Sponsor will provide an alternate method to perform long-term follow-up of any subject that was enrolled and received study medication per regulatory gene therapy requirements.

11.1.12 Publication Policy

Publication of the study results is discussed in the Clinical Trial Agreement. The Sponsor will submit a clinical trial summary report to the relevant regulatory authorities following the end of the study within 1 year of the completion of the study or earlier if required by law.

13 APPENDICES

13.1 Appendix 1 Clinical Laboratory Tests

- The tests detailed in [Table 13-1](#) will be performed by a central laboratory. See Laboratory Manual for further details.
- The use of local laboratories will be permitted, at the investigator's discretion if they are required for immediate clinical decisions
- Local laboratory results are only required in the event that the central laboratory results are not available in time for either study intervention administration and/or response evaluation. If a local sample is required, it is important that the sample for central analysis is obtained at the same time. Additionally, if the local laboratory results are used to make either a study intervention decision or response evaluation, the results must be entered into the CRF.
- The tests detailed in [Table 13.2](#) will be performed by a bioanalytical laboratory. All samples will be sent to the central laboratory for central sample collection management.
- Protocol-specific requirements for inclusion or exclusion of subjects are detailed in [Section 5](#) of the protocol.
- Additional tests may be performed at any time during the study as determined necessary by the investigator or required by local regulations.

Table 13-1 Protocol-Required Laboratory Assessments Performed by a Central Laboratory

Hematology
 
Platelet count
 
Red blood cell (RBC) count
 
Hemoglobin
 
Hematocrit
 
RBC Indices:
 
 MCV
 
 MCH
 
 MCHC
 
 RDW
 
% Reticulocytes
 
White blood cell (WBC) count with differential:
 
 Neutrophils
 
 Lymphocytes
 
 Monocytes
 
 Eosinophils
 
 Basophils
	
Clinical Chemistry
 
Albumin
 
Blood urea nitrogen (BUN)
 
Creatinine
 
Glucose nonfasting
 
Potassium
 
Sodium
 
Chloride
 
Carbon dioxide
 
Calcium
 
Aspartate aminotransferase (AST)
 
Alanine aminotransferase (ALT)
 
Alkaline phosphatase
 
Total and direct bilirubin
 
Total Protein
 
Creatine kinase
 
Lactose dehydrogenase (LDH)
	
Urinalysis
 
Specific gravity
 
pH
 
Glucose
 
Protein
 
Blood
 
Ketones
 
Bilirubin
 
Urobilinogen
 
Nitrite
 
Leukocyte esterase
 
Microscopic examination (if blood or protein is abnormal)


Coagulation
 
aPTT
 
PT
 
INR
 
Fibrinogen
 
D-dimer
	
Other Safety
 
C-reactive protein
 
Ferritin
	
Pregnancy
 
Serum test at screening
 
Urine test at subsequent visits

aPTT = activated partial thromboplastin time, INR = international normalized ratio, LDL= low density lipoprotein, MCH = mean cell hemoglobin, MCHC = mean cell hemoglobin concentration, MCV = mean corpuscular volume, PCR = polymerase chain reaction, PT = prothrombin time, RDW = red blood cell distribution width

Table 13.2 Protocol-Required Laboratory Assessments Performed by a Bioanalytical Laboratory

Cytokines		Other	
GM-CSF	IL-8/CXCL8	Pharmacodynamics: AML in PBMC and BM Biomarkers: AML expression of WT1	Cell kinetics
IFN- γ	IL-10		Immunogenicity
IL-1 α	IL-12(p70)		Exploratory immunology parameters
IL-1 β	IL-13		
IL-4	IL-17A		
IL-5	IL-23		
IL-6	TNF- α		

AML = acute myeloid leukemia; BM = bone marrow; GM-CSF = granulocyte-macrophage colony-stimulating factor; IFN = interferon; IL = interleukin; PBMC = peripheral blood mononuclear cells; TNF = tumor necrosis factor; WT1 = Wilms tumor 1

Investigators must document their review and assessment of abnormal values and clinical significance of each laboratory safety report.

13.3 Appendix 3 ECOG Performance Status

Eastern Cooperative Oncology Group Performance Status Scale

ECOG Performance Status Scale	
Grade	Descriptions
0	Fully active, able to carry on all predisease performance without restriction.
1	Restricted in physically strenuous activity, but ambulatory and able to carry out work of a light or sedentary nature (e.g., light housework, office work).
2	Ambulatory and capable of all self-care, but unable to carry out any work activities. Up and about more than 50% of waking hours.
3	Capable of only limited self-care, confined to bed or chair more than 50% of waking hours.
4	Completely disabled. Cannot carry on any self-care. Totally confined to bed or chair.
5	Dead.

Source: [Oken et al, 1982](#)

ECOG = Eastern Cooperative Oncology Group

13.4 Appendix 4 Hematological Responses Criteria Definitions

Hematological Response	
CR _{MRD}	Less than or equal to 5% blasts in the bone marrow No evidence of extramedullary disease Full recovery of peripheral blood counts: Platelets > 100,000/ μ l, and ANC > 1,000/ μ l MRD not detected [REDACTED]
CR	Less than or equal to 5% blasts in the bone marrow No evidence of extramedullary disease Full recovery of peripheral blood counts: Platelets > 100,000/ μ l, and ANC > 1,000/ μ l MRD detected [REDACTED]
CRh	Less than or equal to 5% blasts in the bone marrow No evidence of extramedullary disease Partial recovery of peripheral blood counts: Platelets > 50,000/ μ l, and ANC > 500/ μ l
CRi*	Less than or equal to 5% blasts in the bone marrow No evidence of extramedullary disease Incomplete recovery of peripheral blood counts Platelets < 100,000/ μ l or ANC < 1,000/ μ l
MLFS	Less than or equal to 5% blasts in the bone marrow No evidence of extramedullary disease Insufficient recovery of peripheral blood counts: platelets \leq 50,000/ μ l and/or ANC \leq 500/ μ l
Partial Remission (PR)	Bone marrow blasts 6-25% with at least a 50% reduction from baseline
Progressive Disease	An increase from baseline of at least 25% of bone marrow blasts or an absolute increase of at least 5,000 cells/ μ L in the number of circulating leukemia cells
Non-Response	None of the above
Hematological Relapse	Proportion of blasts in bone marrow > 5% or Blasts in peripheral blood after documented CR/CRh/CRi
Extramedullary Disease	
Extramedullary disease	If clinical signs of extramedullary lesions are present, responses are assessed by modified Cheson criteria (Cheson et al, 2007).
Molecular Response	
MRD response	MRD < 0.1% [REDACTED]
MRD complete response	MRD not detected [REDACTED]
MRD relapse	Re-appearance of MRD leukemic cells after MRD complete response

ANC = absolute neutrophil count; CR = complete remission; CRh = complete remission with partial hematologic recovery; CRi = complete remission with incomplete recovery of peripheral blood counts; MLFS = morphologic leukemia-free state; MRD = measurable residual disease; PR = partial remission

* When criteria are met for both CRh and CRi, CRh should be reported. When criteria are met for both CRi and blast-free marrow, CRi should be reported.

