8.1 General Study Periods

8.1.1 Screening and Enrollment

Screening

The screening period will be up to 28 days, and a subject that meets all inclusion and none of the exclusion criteria will be enrolled and proceed to the leukapheresis phase in Arm 1 for subjects with AML blasts <5% of bone marrow or in Arm 2 for subjects with AML blasts \geq 5% of bone marrow.

All screening evaluations must be completed and reviewed to confirm that potential subjects meet all eligibility criteria. The investigator will maintain a screening log to record details of all subjects screened and to confirm eligibility or record reasons for screening failure, as applicable. Procedures conducted as part of the subject's routine clinical management (e.g., blood count) and obtained before signing of the informed consent form (ICF) may be utilized for screening or baseline purposes, provided the procedures met the protocol-specified criteria and were performed within the time frame defined in the SoA.

As outlined below, retesting during screening and rescreening is permitted.

Retesting During Screening

Retesting is defined as repeating laboratory tests within the same screening period.

If retesting goes beyond the 28-day screening period, the subject will be classified as a screen failure and will need to go through the rescreening process.

Rescreening

Subjects who fail to qualify for the study based on laboratory tests may be considered for rescreening at the discretion of the investigator if it is considered that the subject's status has changed, and the subject may now qualify for the study. Screening is limited to 2 attempts (initial screening and 1 additional rescreening attempt). A new informed consent is required to be signed prior to rescreening. See Section 11.1.3 for Informed Consent Process details.

Enrollment

The study population will be enrolled in 2 independent Arms.

Subjects in Arm 1 will have < 5.0% AML blasts in bone marrow on locally assessed morphology, and no evidence of blasts in peripheral blood or extramedullary disease (i.e., are in CR/CRi), and MRD identified at a frequency > 0.1% by the central laboratory, [REDACTED]

Subjects in Arm 2 will have $\geq 5.0\%$ AML blasts in BM by locally assessed morphology.

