6.2 Secondary Endpoints

Cell kinetics data profiles will be presented in a data listing based on the CK Analysis Set.

Response is assessed by the investigators per the response criteria defined in Appendix 4 in the protocol, with status and date at each assessment recorded on the “Disease Response Assessment” CRF. Disease response data will be presented in a data listing based on the Safety Analysis Set.

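### The Appendix 4 response table conflicts with Protocol Sections 8.1.1 and 9.4.1 and can misclassify response: circulating blasts, marrow blasts between 5% and 6%, and exactly 5.0%

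*Protocol*

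**What the plan says.** SAP 6.2 sets the standard: "Response is assessed by the investigators per the response criteria defined in Appendix 4 in the protocol".

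In Protocol Section 13.4 (Appendix 4), the five rows CR_MRD-, CR, CRh, CRi and MLFS share one opening: "Less than or equal to 5% blasts in the bone marrow No evidence of extramedullary disease". Each then adds a level of platelet and neutrophil recovery, and CR_MRD- and CR are separated by MRD. PR is "Bone marrow blasts 6-25% with at least a 50% reduction from baseline". Non-Response is whatever fits no row above it.

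Blasts in blood appear in two rows only. The relapse row has marrow blasts above 5%, or "Blasts in peripheral blood after documented CR/CRh/CRi". The progression row has an absolute rise of at least 5,000 circulating leukemia cells per µL.

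Elsewhere, Section 8.1.1 describes Arm 1 subjects at entry as having marrow blasts below 5.0% and "no evidence of blasts in peripheral blood or extramedullary disease (i.e., are in CR/CRi". It admits to Arm 2 at 5.0% or more. Section 9.4.1 dates Arm 1 clinical progression from a marrow blast count of 5.0% or more, or from the start of the next AML therapy. It defines Arm 1 response as CR_MRD- only, and Arm 2 response as CR_MRD-, CR, CRi, MLFS or PR.

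**The concern.** Response, composite CR and duration of response are secondary efficacy endpoints, and all are built from the Appendix 4 categories. A response table should give each subject one category at each visit, rank a deeper reduction no lower than a shallower one, and agree with the thresholds used for entry and progression. This one can fail on each count. A subject with leukemic cells in the blood can be recorded as a complete remission. A near-complete marrow clearance can be recorded as no response. A marrow unchanged since entry can satisfy the remission cut. Investigators who notice these problems will settle them individually, so the recorded categories may not mean the same thing at every site.

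**Working it through.** The plan gives no figure to reproduce on this point. The check reads the Appendix 4 rows literally and classifies test cases.

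**Circulating blasts.** Take marrow blasts of 4%, no extramedullary disease, platelets 150,000/µL, ANC 2,000/µL, MRD detected, and blasts seen in blood.
- Marrow: 4% satisfies "Less than or equal to 5% blasts in the bone marrow".
- Other disease: "No evidence of extramedullary disease" is met. Section 8.1.1 names blood blasts and extramedullary disease as separate conditions, so this line does not cover blood.
- Counts: platelets exceed 100,000 and ANC exceeds 1,000, so recovery is full.
- Result: CR. Under Section 8.1.1 the same subject would not be described as in CR/CRi.

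**Between 5% and 6%.** From a 40% baseline with recovered counts, fall = 1 − (current ÷ 40):

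| Marrow blasts now | Fall from 40% | Appendix 4 category |
|---|---|---|
| 5.0% | 87.5% | CR |
| 5.5% | 1 − 5.5/40 = 86.25% | Non-Response |
| 6.0% | 1 − 6/40 = 85.0% | PR |
| 20% | 1 − 20/40 = 50.0% | PR |

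Every value from 5.1% to 5.9% behaves like 5.5%. The gap costs a subject a PR only when the fall is at least 50%, that is, when baseline is at least 5.1 ÷ 0.5 = 10.2% (for 5.1%) to 5.9 ÷ 0.5 = 11.8% (for 5.9%).

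**Exactly 5.0%.**

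| Rule | Cut | Is 5.0% included? |
|---|---|---|
| Remission rows, Section 13.4 | ≤5% | Yes |
| Arm 2 entry, Section 8.1.1 | ≥5.0% | Yes |
| Arm 1 clinical progression, Section 9.4.1 | ≥5.0% | Yes |
| Relapse, Section 13.4 | >5% | No |

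An Arm 2 subject who enters at 5.0%, with an unchanged marrow and no extramedullary disease, meets a remission row at every count level tried: CR at platelets 150,000 and ANC 2,000; CRh and CRi at 70,000 and 800; CRi and MLFS at 30,000 and 300. An Arm 1 subject at 5.0% meets the remission marrow cut and the clinical progression cut at the same visit, but not the marrow part of relapse.

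**Size.** Under the protocol's planned rates, one subject in a 9-subject expansion cohort is 1/9 = 11.1 percentage points. Pooling six escalation subjects at the same dose would give 1/15 = 6.7 points, but Section 9.4.1 summarizes escalation by cohort and expansion by arm, so that pooled rate is not planned. Section 4.1 requires six subjects at the dose before expansion only for Arm 1. SAP Section 7 drops objective response rate, composite CR rate, duration of response and time to progression, because 2 subjects had received NTLA-5001 when the study was terminated. Neither shift will therefore appear in any output.

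**The case against.** The strongest reply is that little now depends on the table. Only a listing remains, 2 subjects were treated, and nothing shows that either fell in one of these zones. That stands. A reader might infer that responses in this trial were misclassified, or that reported rates are off by 7 or 11 points; the documents support neither.

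The gap between 5% and 6% depends on how blasts are recorded. A reader might take the 5.0% thresholds as proof of one-decimal reporting, but no section sets a precision for local morphology, and the protocol also writes 5% in places. With whole-percent reporting, remission and PR adjoin and the gap disappears.

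A reader might also infer that a first response can be a relapse at the same visit. It cannot, because the relapse row applies only after CR, CRh or CRi has been documented. The overlap can arise only at a later visit, when a subject in documented remission shows blood blasts and still meets the CR row.

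Arm 1 is barely affected. Its response also requires undetected MRD, and its duration of response ends when MRD reappears. The Arm 1 and Arm 2 overlaps at the boundary need a reading of exactly 5.0%.

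Finally, Section 9.4.1 also has investigators assess each post-baseline marrow by published ELN recommendations. Their text is not in these documents, so whether they address blood blasts cannot be settled here. Section 9.4.1 nevertheless describes Section 13.4 as a modified version, and the SAP names Appendix 4, so the reference does not repair the table.

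**Conclusion.** The point holds as a defect of definition. Appendix 4 omits a condition that Section 8.1.1 treats as part of CR/CRi, leaves values above 5% and below 6% without a response category, and overlaps at exactly 5.0% with Arm 2 entry and Arm 1 clinical progression. No other section cures this. The circulating-blast problem bears mainly on Arm 2. The gap assumes decimal recording. How often a subject would have circulating blasts with marrow blasts of 5% or less is not given, so no expected number of affected subjects can be stated. For the analyses still planned, the consequence is limited to the meaning of the categories in the investigator-assessed listing for 2 subjects.

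**What to change.** Reconcile Appendix 4 with Sections 8.1.1 and 9.4.1:

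1. Use one side of 5.0% throughout: remission below 5.0%; Arm 2 entry, Arm 1 clinical progression and relapse at 5.0% or more.
2. Start PR where remission ends, so that no value lies between them.
3. Add absence of circulating blasts at least to CR_MRD-, CR, CRh and CRi. Decide MLFS explicitly: Section 8.1.1 speaks only of CR/CRi and the relapse row omits MLFS, so the documents do not settle it.
4. State the category for a subject with marrow blasts below 5.0% and circulating blasts. Step 3 alone is not enough. If every remission row excluded blood blasts and PR ran from 5.0% to 25%, a fall from 40% to 4% with circulating blasts would be Non-Response, while a fall from 40% to 20% with circulating blasts would still be PR, because PR has no blood criterion. The stated category must not rank below that smaller reduction.

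In the SAP, check both treated subjects' listed categories against the reconciled table and footnote any difference. Label any per-subject rate shift as applying only to the protocol's planned rates.

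The cost is wording in the protocol and the CRF guidance, and possibly slightly fewer responders. No new sampling is needed: Section 8.8 already assesses AML blasts in blood and marrow, and the Schedule of Activities pairs PBMC morphology with marrow sampling. The blood finding should come from those sources, since the central differential in Table 13-1 lists no blast count.
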